## 12.2. Further Details and Clarifications on the Serious Adverse Event Definition

### 12.2.1. Guidance on Safety Monitoring

#### Guidance on Monitoring Participants with Elevated Liver Function Tests

Liver enzymes (ALT, AST, gamma glutamyl transpeptidase [GGT], and ALP) as well as total bilirubin will be measured at each trial visits 1, 3, and 5.

In any case of elevated ALT or AST to a level exceeding  $\geq 2 \times$  the upper limit of normal (ULN) (including participants whose baseline ALT or AST levels are  $\geq 2 \times$  and  $\leq 3 \times$  the ULN, who may be enrolled in the trial), a thorough medical history and physical examination with a focus on liver disease should be undertaken. In addition, the participant should be instructed to refrain from alcoholic beverages.

In case of symptoms compatible with drug-induced liver injury during the trial, participants will be instructed to return to the trial center for an unscheduled visit or to go to the emergency room to measure liver enzymes as soon as possible. Solitary elevations of total bilirubin, not accompanied by elevations of ALT or AST should be managed according to the discretion of the treating physician.

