### 5.2. Rationale for Trial Population

See Section [4.2](#).

Prospective waivers (exceptions) from trial inclusion and exclusion criteria to allow participants to be randomized/enrolled are not granted by Teva (Section [11.2](#)).

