## 5.4. Exclusion Criteria

Participants will be excluded from participating in this trial if they meet any of the following criteria:

- a. The participant is using medications containing opioids (including codeine) or barbiturates (including Fiorinal®, Fioricet®, or any other combination containing butalbital) for the treatment of migraine during the 3 months prior to the day of the screening visit.
- b. The participant has used an intervention/device (eg, scheduled nerve block or transcranial magnetic stimulation) for the treatment of migraine or in the head or neck area for any condition during the 2 months prior to the day of the screening visit.
- c. The participant has any clinically significant cardiovascular (including congenital cardiac anomalies or thromboembolic events), endocrine, gastrointestinal, genitourinary, hematologic, hepatic, immunologic, neurologic, ophthalmic, pulmonary, renal disease, or complications of an infection, at the discretion of the Investigator.
- d. [Revision 01] The participant has a current history of a clinically significant psychiatric condition, at the discretion of the investigator. Any prior history of a suicide attempt, or a history of suicidal ideation with a specific plan within the past 2 years must be excluded.
- e. The participant has an ongoing infection or a known history of human immunodeficiency virus (HIV) infection, tuberculosis, Lyme disease, chronic hepatitis B or C, or a known active infection of COVID-19.
- f. The participant has a past or current history of cancer.
- g. The participant is pregnant or nursing.
- h. The participant has a history of hypersensitivity reactions to injected proteins, including mAbs, or a history of Stevens-Johnson Syndrome or toxic epidermal necrolysis syndrome, or the participant is concomitantly using lamotrigine.
- i. The participant has participated in another trial of an IMP (or a medical device) within the 30 days (or 90 days for biologics) or 5 half-lives previous to the day of the screening visit (whichever is longer), or is currently participating in another trial of an IMP (or a medical device).
- j. The participant has had exposure to a mAb targeting the CGRP pathway (erenumab, eptinezumab, galcanezumab, fremanezumab) during the 6 months previous to the day of the screening visit.
- k. Previous participation in the Phase 1 pharmacokinetics trial (Trial TV48125-CNS-10141).

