- l. In the judgment of the Investigator, the participant has an abnormal finding on the baseline 12-lead ECG considered clinically significant.
- m. In the judgment of the Investigator, the participant has a significantly abnormal finding during the 28-day baseline period, including hematology, blood chemistry,

coagulation tests, or urinalysis values/findings (abnormal tests may be repeated for confirmation).

- n. The participant has hepatic enzymes (alanine aminotransferase [ALT], aspartate aminotransferase [AST], alkaline phosphatase [ALP]) more than  $1.5 \times$  the upper limit of normal (ULN) during the 28-day baseline period, after confirmation in a repeat test, or suspected hepatocellular damage that fulfills the criteria for Hy's law.
- o. The participant has serum creatinine more than  $1.5 \times$  the ULN, clinically significant proteinuria (urine dipstick +4), an estimated glomerular filtration rate (eGFR) of  $<75$  mL/min/1.73m^2, as calculated by the revised Schwartz formula (eGFR=[0.413×Ht]/serum creatinine), or evidence of renal disease during the 28-day baseline period.
- p. The participant has any history of alcohol or drug abuse. The definition of alcohol or drug abuse, including marijuana, is based on the Investigator's clinical judgement.
- q. In the judgment of the Investigator, the participant cannot fully participate in or successfully complete the trial for its full duration for any of the following reasons:
  - The participant is mentally or legally incapacitated, or unable to give assent/consent for any reason.
  - The participant is in custody due to an administrative or a legal decision or is in residential treatment.
  - The participant /caregiver is unable to be contacted in case of emergency.
  - The participant has any other condition, which, in the opinion of the Investigator, makes the patient inappropriate for inclusion in the trial.
  - The participant is a relative of a trial center or Sponsor employee who is directly involved in the trial.
- r. Vulnerable participants (eg, people kept in detention) whose vulnerability is based on a condition other than the age required for trial eligibility.
- s. The participant received a live attenuated vaccine (eg, intranasal flu vaccine, and measles, mumps, and rubella vaccine) within the 12-week period prior to screening.

**Note:** If a medical need arises during the trial, the participant may receive a live attenuated vaccine.

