### **8.3.4.1. Serum Chemistry, Hematology, Coagulation, and Urinalysis**

All clinical laboratory test results outside of the reference range will be judged by the Investigator as belonging to one of the following categories:

- abnormal and not clinically significant
- abnormal and clinically significant

A laboratory test result that is judged by the Investigator as clinically significant will be recorded both on the source documentation and the CRF as an adverse event and monitored as described in Section 8.4.5. An adverse event may include a laboratory or diagnostic test abnormality (once confirmed by repeated testing) that results in the withdrawal of the participant from the trial, the temporary or permanent withdrawal of IMP or medical treatment, or further diagnostic work-up. (Note: Abnormal laboratory or diagnostic test results at the screening visit that preclude a participant from entering the trial or receiving IMP are not considered adverse events.)

In addition, potentially clinically significant values will be predefined by the Sponsor for selected laboratory parameters and will be detailed in the statistical analysis plan.

Clinical laboratory tests (serum chemistry, hematology, coagulation, and urinalysis) will be performed at the time points detailed in [Table 1](#). In case of suspected hepatitis, HIV, or Lyme disease, a blood sample may be taken at screening at the discretion of the Investigator. Baseline is screening (visit 1). Clinical laboratory tests will be performed using the central laboratory. Specific laboratory tests to be performed are listed in Section 13.2. Note, reflex tests (eg, red blood cell [RBC] shapes, RBC morphology, and other microscopic findings) may be triggered automatically.

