#### Elevation of Either ALT or AST to $\geq 3 \times$ ULN

Confirmation is required prior to IMP discontinuation in cases of elevation of either ALT or AST  $\geq 3 \times$  ULN (Note: In cases of elevation of ALT or AST  $\geq 8 \times$  the ULN, no confirmation is required prior to IMP discontinuation, but the assessments below should be performed). The following procedures should be followed:

- The day in which the abnormal value is received from the laboratory will be considered as day 0.
- The Investigator should repeat the test for confirmation purposes (this may be performed in a local laboratory along with complete blood count [CBC] and differential to assess for eosinophilia. In general, in case a blood sample is sent to a local laboratory, the following assessments [and reference ranges] are mandatory: ALT [serum glutamic pyruvic transaminase], AST [serum glutamic oxaloacetic transaminase], ALP, total bilirubin, CBC [with differential for eosinophil count, separate tube], and INR [separate tube; not to be sent in a confirmatory test]). The Investigator should also question the participant regarding symptoms.

---

 In case total bilirubin is  $>$ ULN, then direct bilirubin will be checked.

 Thorough medical history with a focus on liver disease: personal or family history of liver disease; personal history of a systemic disease with potential liver involvement; exposure to alcohol, medications (prescription or over the counter), herbal preparations, dietary supplements, recreational drugs, special diets, or environmental chemical agents; potential exposure to infectious agents (eg, travel to developing countries, history of potential exposure to blood or blood products, high-risk sexual relations); and any additional information deemed relevant by the Investigator. Physical examination, including signs of chronic liver disease.

The abnormality will be regarded as confirmed in each of the following scenarios:

- the baseline value was within the normal range and ALT or AST is still  $\geq 3 \times$  the ULN
- the baseline value was above the ULN and ALT or AST is  $\geq 2 \times$  the baseline value

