### **Additional Tests/Evaluations**

Upon confirmation of the abnormality as noted above, the following additional evaluations should be performed and results should be recorded in the CRF:

- serology for hepatitis A (antibody and immunoglobulins M and G), B (core antibody total, core immunoglobulin M, and surface antigen), and C viruses (central laboratory)
- serology for autoimmune hepatitis: anti-nuclear antibodies (titer), anti-smooth muscle antibodies, and anti-liver kidney microsomal antibodies (central laboratory); further testing may be required in case of a positive result for hepatitis B or C
- ultrasound examination of the liver and biliary tract at the Investigator's discretion
- other diagnostic tests/consultations as deemed necessary by the Investigator (eg, serology for hepatitis E virus in case of travel to endemic geography)
- observation and follow-up (to be performed after the abnormality was confirmed as above)

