4.2. Specification of Baseline Values

Participants will complete electronic headache diary entries daily for the 28-day run-in period, subjectively rating their headaches as mild, moderate, or severe and enter headache information (ie, occurrence of headache, duration of headache, maximum severity of headache, and acute headache medication use) about the previous day into the electronic headache diary device. If the participant is unable to complete the diary themselves then a parent/caregiver will complete the diary for them. Headache severity is collected in the diary on an 11-point numerical rating scale where mild is defined as a rating of 1-3, moderate as 4-6 and severe as 7-10. If the run-in period is greater or less than 28 days, the baseline values for calculating the change from baseline of the monthly values of the efficacy variables will be normalized to **28** days.

The efficacy baseline values during the 28-day run-in period derived from the e-diary include

- total number of migraine days
- total headache days of at least moderate severity
- total number of days of use of any acute headache medication
- total headache days of any severity
- total number of days of use of acute headache medications (triptans and ergot compounds, NSAIDs or paracetamol) for the group of participants who use acute headache medications at baseline
- total number of days with nausea or vomiting
- total number of days with photophobia and phonophobia

Other efficacy baseline values that will be measured on day 1 before the 1st IMP administration include

- disability score, as measured by the PedMIDAS assessment ([Appendix C](#))
- quality of life, as measured by the PedsQL questionnaire ([Appendix D](#))

Otherwise, baseline value will be the last non-missing value prior to the 1st dose of IMP, unless otherwise noted.

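### Protocol Section 12.2.1 says children with baseline ALT or AST of 2x to 3x ULN may be enrolled, but exclusion n bars any value above 1.5x ULN confirmed on repeat (minor correction)

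*Protocol*

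**What the plan says.** **Eligibility.** Protocol Section 5.4 opens with "Participants will be excluded from participating in this trial if they meet any of the following criteria". Criterion n applies when ALT, AST or ALP is more than 1.5 times "the upper limit of normal (ULN) during the 28-day baseline period, after confirmation in a repeat test". Section 5.2 adds: "Prospective waivers (exceptions) from trial inclusion and exclusion criteria to allow participants to be randomized/enrolled are not granted by Teva". Section 11.2 repeats that position.

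**Liver-monitoring guidance (Section 12.2.1).** The paragraph that asks for a history and examination at 2x ULN or more contains a bracket. It takes in children whose baseline ALT or AST is 2x to 3x ULN: "the ULN, who may be enrolled in the trial), a thorough medical history and physical examination". The heading of the 3x-to-5x ULN tier raises the tier's lower limit to above 3.5x ULN when the baseline is above 2.5x ULN.

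**Confirmation.** An elevation to 3x ULN or more has to be confirmed by a repeat. With a normal baseline, the repeat must still be at 3x ULN or more. The other scenario is that "the baseline value was above the ULN and ALT or AST is" at least twice that baseline. The work-up then follows: "Upon confirmation of the abnormality as noted above, the following additional evaluations should be performed". It includes hepatitis and autoimmune serology.

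**Baseline.** Section 8.3.4.1 sets the laboratory baseline at the visit 1 screening value. The general analysis rule in SAP Section 4.2 reads: "baseline value will be the last non-missing value prior to the 1st dose of IMP, unless otherwise noted".

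**The concern.** Two places in Section 12.2.1 presuppose enrolled children whom Section 5.4 keeps out. Both are current Amendment 09 text, not entries in the amendment log. Section 5.4 governs entry, so the appendix is the part that is wrong. Even so, a site reading the appendix is told that a child at 2x to 3x ULN is acceptable.

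One kind of child can properly enter with a visit 1 value in that range: one whose repeat falls to 1.5x ULN or below, so that the elevation is not confirmed. The bracket is not limited to this child. For this child the visit 1 baseline also has a clinical effect. The confirmation rule works in multiples of baseline, so a transient high screening value raises the level at which a later elevation counts as confirmed and the work-up begins.

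**Working it through.** There is no plan figure to reproduce. The check compares the thresholds and then applies the confirmation rule.

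**Step 1. Compare the ranges (multiples of ULN).**
- Exclusion n: a value above 1.5, once confirmed on repeat, excludes.
- Section 12.2.1 bracket: baselines from 2 to 3 may enter.
- Section 12.2.1 tier heading: special rule for baselines above 2.5.

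The whole range 2 to 3 lies above 1.5, so every confirmed value in it meets exclusion n. The texts can be reconciled only if the repeat is 1.5 or below, and neither place in Section 12.2.1 says so.

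**Step 2. Confirmation level.** For a baseline *b* above ULN, the level is 2 × *b*. For a normal baseline it is 3.

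| Baseline *b* (x ULN) | Confirmation level 2*b* (x ULN) |
|---|---|
| 1.2 | 2.4 |
| 1.5 | 3.0 |
| 2.0 | 4.0 |
| 2.5 | 5.0 |
| 3.0 | 6.0 |

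At the entry limit of 1.5 the level is 3.0, which is exactly where the confirmation procedure starts. The two rules therefore fit together for any child whose baseline respects exclusion n. They separate only for baselines above 1.5.

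**Step 3. The child who can properly enter.** Let *v* be the visit 1 value and *r* the repeat, with *r* at 1.5 or below.

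| *v* | *r* | Level with visit 1 as baseline (2*v*) | Level with repeat as baseline (2*r*) |
|---|---|---|---|
| 2.0 | 1.2 | 4.0 | 2.4 |
| 2.5 | 1.4 | 5.0 | 2.8 |
| 2.8 | 1.4 | 5.6 | 2.8 |
| 3.0 | 1.5 | 6.0 | 3.0 |

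If *r* is within the normal range, the level is 3.0. So for any *v* above 1.5, the repeat gives a level of at most 3.0, and visit 1 gives more than 3.0.

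**Step 4. Rules that do not depend on baseline.** The stopping rules in Sections 7.1 and 12.2.1 are multiples of ULN: 3x with raised INR or bilirubin, 3x with symptoms, 5x to below 8x lasting two weeks or more, and 8x. The request for a history and examination at 2x ULN or more also does not depend on baseline.

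**The case against.** The bracket is permissive, exclusion n operates only after a repeat, and the laboratory baseline is visit 1. Read together, a child at 2x to 3x ULN at visit 1 whose repeat falls may enter with that baseline, so the defect could be called a missing qualifier. This reading is available, and it supports limiting the bracket as an alternative to deleting it. It does not make the text correct, because the bracket states no such limit and the tier heading makes the same assumption.

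The practical harm is also limited. Scheduled liver tests are at visits 1, 3 and 5 and doses at visits 2, 3 and 4. A scheduled on-treatment result can therefore affect at most the visit 3 dose, if it is back in time, and the visit 4 dose. Section 8.4.5 allows extra laboratory tests for an adverse event, and Section 7.1 calls for stopping the drug when continuing is not in the child's interest. All of this stands.

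Three stronger readings are tempting, and the documents do not support them:
- **That the protocol and SAP conflict on baseline.** SAP Section 4.2 is an analysis rule that yields where something else is noted. Section 8.3.4.1 is the specific laboratory rule, and nothing sends an investigator to the SAP to apply Section 12.2.1.
- **That the child would stay on drug until 4x to 6x ULN.** The confirmation subsection does ask for confirmation before discontinuation below 8x ULN. The stopping rules, however, require immediate discontinuation and carry no baseline condition.
- **That ineligible children were enrolled, or that efficacy results are affected.** No such child is identified. The full analysis set is defined by dosing and diary days. Section 11.2 and SAP Section 5.9 already require eligibility deviations to be reported, reviewed and listed.

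**Conclusion.** The point holds as a minor correction: Section 12.2.1 is wrong as written against exclusion n. For a child with a visit 1 value of 2x to 3x ULN that was not confirmed on repeat, the confirmation level is 4x to 6x ULN. It would be at most 3x ULN if the repeat were the baseline. The consequence is a possible delay to the additional work-up, with the ULN-based stopping rules still in force. The primary analysis on the full analysis set is unaffected.

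This assumes that visit 1 is used as baseline, as Section 8.3.4.1 says, and that such children exist. The documents do not give their number, which is probably small.

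**What to change.** 1. In the Section 12.2.1 paragraph on monitoring elevated liver tests, delete the bracket about baselines of 2x to 3x ULN, or limit it to a screening elevation that was not confirmed on repeat.
2. In the heading of the 3x-to-5x ULN tier, delete the bracket for baselines above 2.5x ULN, so that the tier starts at 3x ULN for everyone.
3. Add to Section 12.2.1: *Where a screening ALT or AST above 1.5x ULN fell to 1.5x ULN or below on repeat, the repeat value is the baseline for all rules in this section.*

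The condition on the repeat in item 3 is needed. Without it, a child entered in breach with 1.8x and then 2.9x ULN would see the confirmation level rise from 2 × 1.8 = 3.6x to 2 × 2.9 = 5.8x ULN.

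Item 3 has one effect in the other direction. If the repeat is within the normal range, the level for continued follow-up of a persisting abnormality becomes 3x ULN in place of 2x ULN, the same as for any child with a normal baseline.

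Exclusion n stays as it is, and no new deviation listing is needed. The cost is two text edits and one sentence in an appendix, with no added visits or participants. The note to file attached to the SAP says the trial analysis has been conducted. If enrolment has closed, the correction belongs in a note to file.

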## 8. TRIAL ASSESSMENTS AND PROCEDURES

### 8.1. Screening/Baseline Assessments and Procedures

A signed and dated ICF will be obtained before screening procedures commence (see Section 10.3). Procedures performed at screening are listed in [Table 1](#) and Section 13.9.

Evaluations obtained as part of routine medical care and performed during the screening period may be used in place of the protocol-specific evaluations. Participants will acknowledge and agree to the possible use of this information for the trial by giving informed consent.

Participants may have individual parameters retested at the discretion of both the Investigator and the Sponsor (also see Section 5.6).

Participants who fulfil the inclusion criteria and meet none of the exclusion criteria at the screening visit may be enrolled in the trial.

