### **ALT or AST $\geq 3 \times$ ( $>3.5 \times$ the ULN if the Baseline Value Is $>2.5 \times$ the ULN) but Less Than $5 \times$ the ULN**

In addition to the above procedures required for any elevation to levels  $>3 \times$  the ULN:

- ALT, AST, GGT, ALP, total and direct bilirubin, CBC and differential (to assess for eosinophilia), and INR should be monitored on days 5 ( $\pm 2$  days), 8 ( $\pm 2$  days), 14 ( $\pm 3$  days), and 28 ( $\pm 3$  days). On at least 1 of these days, the test should be performed centrally. (The INR should be sent to a local laboratory only.)
- In cases where a local laboratory is used, the results should be recorded in the CRF, accompanied by the reference range of the relevant measurements.
- Should the abnormality ( $\geq 3 \times$  the ULN in case baseline was within the normal range or  $\geq 2 \times$  the ULN in case the baseline value was above ULN but still  $<5 \times$  the ULN) persist further, the participant will be followed according to the Investigator's discretion, but a blood sample for ALT, AST, GGT, ALP, and total and direct bilirubin should be sent to the central laboratory at least once a month.

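### For ALT or AST confirmed at 2 to 3 × ULN at baseline, exclusion criterion n bars the participant while the liver appendix (Protocol 12.2.1) allows enrolment

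*Protocol*

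**What the plan says.** **Eligibility text.** Protocol 5.4 opens with "Participants will be excluded from participating in this trial if they meet any of the following criteria". Criterion n covers ALT, AST and ALP and sets its limit at 1.5 times, measured against "the upper limit of normal (ULN) during the 28-day baseline period, after confirmation in a repeat test". Protocol 8.1 repeats the principle: only those who "meet none of the exclusion criteria at the screening visit may be enrolled in the trial". Protocol 5.2 rules out prospective waivers.

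**Liver appendix.** Protocol 12.2.1 asks for a liver-focused history and examination when ALT or AST reaches 2 × ULN, "including participants whose baseline ALT or AST levels are" at least 2 × and at most 3 × ULN, "who may be enrolled in the trial". No repeat-test condition is attached.

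Two further rules in 12.2.1 depend on baseline:

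- An on-treatment elevation of 3 × ULN or more counts as confirmed if the value is still at least 3 × ULN (normal baseline) or at least twice the baseline value (baseline above ULN).
- The follow-up tier that normally begins at 3 × ULN begins above 3.5 × ULN "if the Baseline Value Is" above 2.5 × ULN.

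**Definition of baseline.** Protocol 8.3.4.1 takes screening (visit 1) as the laboratory baseline. SAP 4.2 defaults to the last non-missing value before the first dose unless otherwise noted.

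**The concern.** Both texts are in the current Amendment 09 body, and no section says which takes precedence. Protocol 8.4.1.2 sends investigators to Section 12.2 for liver monitoring, so sites are expected to read the enrolment statement.

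Two things are at stake. The first is participant safety: a child enrolled on the strength of the appendix would be followed under confirmation and follow-up levels that rise with baseline. The second is deviation classification. Protocol 11.2 counts departures from the eligibility criteria among possible important deviations, and SAP 3.4 removes participants with important eligibility deviations from the per-protocol set. If one section permits what another forbids, it is open to argument whether such a participant is a deviation at all.

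**Working it through.** There is no plan figure to reproduce. The check compares thresholds, with b the baseline ALT or AST as a multiple of ULN.

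**1. Do the ranges overlap?** Criterion n permits b ≤ 1.5 once a repeat has settled the value. The appendix permits 2 ≤ b ≤ 3. The lowest appendix value, 2, already exceeds 1.5, so the ranges share no point.

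| Baseline ALT or AST | Criterion n | Section 12.2.1 |
|---|---|---|
| ≤ 1.5 × ULN | not excluded | silent on enrolment |
| above 1.5 to below 2 × ULN, confirmed | excluded | silent: no explicit conflict |
| 2 to 3 × ULN, confirmed on repeat | excluded | may be enrolled: **conflict** |
| 2 to 3 × ULN at visit 1, repeat ≤ 1.5 × ULN | not excluded | may be enrolled: compatible |

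The last row depends on Protocol 8.3.4.1. With visit 1 as the laboratory baseline, a child whose repeat is low still has a baseline of 2 to 3 × ULN. Under the SAP 4.2 default, a later pre-dose repeat would replace that value. For ALP there is no conflict, because the enrolment statement covers only ALT and AST.

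**2. What follows for a child enrolled under the appendix?** For a baseline above ULN, the confirmation level is 2 × b:

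- b = 1.5 (criterion n's limit): 2 × 1.5 = 3 × ULN, the same as for a normal baseline
- b = 2: 2 × 2 = 4 × ULN
- b = 2.5: 2 × 2.5 = 5 × ULN
- b = 3: 2 × 3 = 6 × ULN

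Within criterion n's limit the baseline-dependent rule never asks for more than 3 × ULN. Across the appendix's range it asks for 4 to 6 × ULN. The additional hepatic evaluations start on confirmation, and confirmation is required before IMP is stopped for elevations of 3 × ULN or more, except at 8 × ULN or more. Both steps therefore come at a higher enzyme level for such a child.

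**3. Is the enrolment phrase isolated?** The doubling rule could be meant for baselines between 1 and 1.5 × ULN, which criterion n allows. The separate tier for baselines above 2.5 × ULN has no such use. Under criterion n it could apply only to an unconfirmed visit 1 value. It therefore builds on the same premise as the enrolment phrase.

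**The case against.** Section 5.4 is the eligibility section. It excludes on any one criterion, waivers are refused, and Table 1 has eligibility confirmed before randomization. The conflicting words are a parenthesis in monitoring guidance, and a site is more likely to follow Section 5.4. That lowers the chance of harm, but the two texts still disagree.

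A reader might infer that no reading reconciles the texts, or that they conflict over the whole span from 1.5 to 3 × ULN. Neither is supported. An unconfirmed visit 1 elevation fits both, and the appendix grants nothing between 1.5 and 2 × ULN. What remains is that the appendix does not confine itself to unconfirmed values.

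A reader might also infer that the appendix relaxes the stopping thresholds. It does not. The 3.5 × ULN figure starts a follow-up schedule, and the numeric stopping thresholds in Protocol 7.1 and 12.2.1 are the same for every baseline. What varies is the confirmation step that precedes discontinuation below 8 × ULN.

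Finally, much of the material for a listing is already planned: SAP 5.9 lists protocol deviations and SAP 8.6 lists all laboratory results. The note to file of 29 May 2025 says the analysis was conducted, so rewording may come too late to affect enrolment. Both points reduce the benefit of a fix. However, neither planned listing brings together the screening enzyme value, its repeat and the resulting deviation decision.

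**Conclusion.** The contradiction holds for ALT or AST confirmed on repeat at 2 to 3 × ULN in the baseline period, and only there. Its practical consequence, if anyone entered on that basis, is confirmation and work-up at 4 to 6 × ULN rather than at 3 × ULN.

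The documents give no count of such participants, and it may be zero. Nothing in them shows that an ineligible child was enrolled. The effect on the primary analysis is nil, because membership of the full analysis set (SAP 3.3) requires a dose of IMP and at least 10 postbaseline diary days and does not depend on eligibility deviations. Only the repeat of the primary and secondary analyses in the per-protocol set (SAP 6.1) could change.

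The conclusion assumes that baseline in Section 12.2.1 means the visit 1 value, as Protocol 8.3.4.1 says. Under the SAP 4.2 default the compatible case could narrow, and the conflict for confirmed values would remain. This review takes no position on which enzyme limit is right.

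**What to change.** Reconcile four places: criterion n in Protocol 5.4 and, in 12.2.1, the enrolment parenthesis, the confirmation rule based on twice the baseline value, and the follow-up tier for baselines above 2.5 × ULN. One baseline-enzyme rule should apply throughout, and it should state how an unconfirmed visit 1 elevation is treated and which value then counts as baseline. The choice of limit is for the sponsor and its clinical experts.

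Produce one listing of every randomized participant whose baseline ALT, AST or ALP exceeded criterion n's limit. It should show the visit 1 value, the repeat result, and the deviation classification used for the per-protocol set. If the listing is empty, say so in the clinical study report.

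The cost is a wording change by amendment or administrative letter (or an explanation in the study report if enrolment has closed) and one listing from data already collected. Sample size, randomization and the primary analysis do not change.
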